Implementation

Modifications of protocol text are shown in Sections A and B of this LoA, using strikethrough for deletions and bold type for additions where appropriate. Within these sections, modifications are generally shown in order of appearance in the protocol. Operational guidance for conducting study visits and procedures during the COVID-19 pandemic is provided in Section C of this LoA; conventions for use of strikethrough and bolding do not apply in this section.

A. Protocol Team Roster Updates

To reflect current membership, the protocol team roster is updated as follows:

Protocol Statisticians

[name], MS Statistical and Data Management Center (SDMC) Frontier Science Foundation [name] [contact] [name]

E-mail: [contact]

Protocol Data Managers

[name] **Frontier Science Foundation** [name]

[contact] [name]

E-mail: [contact]

[name] Frontier Science Foundation [name] [contact] [name]

E-mail: [contact]

Laboratory Data Coordinator Manager

[name], MSW [name], MA, PhD **Frontier Science Foundation**

Frontier Science and Technology Research

Foundation (FSTRF), Inc.

[name]

[contact] [name] E-mail: [contact]

[contact]

Protocol Pharmacists

[name], RPh Pharmaceutical Affairs Branch, Division of AIDS/OCSO/NIAID/NIH [name] **[name]** [name]

[contact]

E-mail: [contact]

Laboratory Center Representative

[name], BS, CCRA IMPAACT Laboratory Center Children's Hospital Los Angeles

[contact]

Email: [contact]

[name], MT(ASCP) **IMPAACT Laboratory Center University of California Los Angeles** [name]

[name] [contact]

E-mail: [contact]

B. Clarifications and Corrections of Protocol Text from Corrected CM #1, dated 26 September 2018, and CM #2, dated 6 January 2019

1. In Sections 2.2, 8.2, and 8.6, the following updates are incorporated to correct inconsistencies in the specified timing of safety and tolerability analyses:

Section 2.2, Secondary Objective 5

To determine the extended long term ($\geq > 48$ weeks) safety, tolerability and efficacy of DTG in HIV-1 infected infants, children and adolescents.

Section 8.2.1.1 (section heading)

Toxicity through Weeks 24 and 48

Section 8.2.3.1 (section heading)

Toxicity through week 48 and beyond Week 48

Section 8.6.2.1 (section heading)

Primary Analyses (performed on data through the Week 24 and 48 visits)

Section 8.6.2.2, Key Secondary Analyses, Safety

Safety assessments will be performed on data collected through Week 48 and long term data. These analyses will be similar to the Weeks 24 analyses described in Section 8.6.2.1 above. In addition, these analyses will also be performed with participants classified by weight band.

- 2. In Section 3.1, the following updates are incorporated to clarify screening and enrollment procedures for weight-band groups:
 - Stage 1 Full Cohort and Weight-band Analysis

The study aims to ensure that adequate numbers of participants are enrolled into each of the age-defined cohorts as well as each of the weight-band groups. To this end, once 10 participants with evaluable data are enrolled into a cohort, additional enrollments into that cohort are only permitted if a participant will be contributing to achieve the minimum enrollment of 8 evaluable in a weight-band group. To ensure continuous enrollment into cohorts during Stage 1, enrollment does not close until it has been confirmed that 8 participants with evaluable data have been enrolled and completed PK and safety assessments into a weight band. Up to A maximum of an additional 2 participants can be enrolled while waiting for determination that the data from the minimum of 8 participants in a given weight-band group are evaluable. these results to become available.

Participants are enrolled into Stage I weight-band groups based on their weight at enrollment. However, if a participant is eligible for a given weight-band group by weight at screening but then has a different weight on the day of enrollment that places him/her into a different weight-band group, he/she will be allowed to enroll in Stage I, even if the minimum accrual targets for that weight-band group have been met. In this case, the participant will contribute to the Stage I full cohort and weight-band analysis based on weight at enrollment.

3. In Section 6.1.8 and Appendix IG, the following updates are incorporated to clarify the timeline for resuming once daily dosing of dolutegravir after discontinuation of rifampin-containing tuberculosis treatment:

Section 6.1.8, Management of Participants Co-infected with TB, last bullet, second sentence: Approximately two weeks after Upon discontinuation of the rifampin containing anti-TB therapy, the participant's DTG dose will revert back to once daily administration unless on EFV, FPV/r, or TPV/r.

Appendix IG, note directly following Schedule of Evaluations, third sentence:

Approximately two weeks after Upon discontinuation of the rifampin containing anti-TB therapy, the participant's DTG dose will revert back to once daily administration.

4. In Section 5.2.3, second paragraph and first and second bullets, the following updates are incorporated to correct an inconsistency in dispensing procedures for dolutegravir dispersible tablets:

In Stage I and Prior to intensive PK sampling in Stage I, each tablet is to be dispersed using 2 to 5 mL of water. There are two options for dispensing described below.

- Option 1: for older children, pour drinking water into the dosing cup. For 1-2 tablets use 5mL of water. For 3-4 tablets use 10mL of water and for 5-6 tablets use 15 of water. For 1-3 tablets use 5mL of water, for 4-6 tablets use 10mL of water. Add the prescribed number of tablets to the water. Swirl the cup gently for 1-2 minutes to fully disperse the tablets. The medicine will be cloudy. If any lumps of tablet remain, swirl the cup gently until they are gone. Give Administer the prepared dose to the child. Rinse the dosing cup before next use. Pour an additional 5 mL of water in the dosing cup, swirl the cup gently for approximately 15 seconds and administer the entire volume to the participant. Wash the dosing cup immediately after administration, allow to dry and store for the next use.
- Option 2: for infants and younger children, prepare medicine in dosing cup as directed in Option 1. Draw up all the medicine into the syringe. Place the tip of the syringe against the inside of the infant's cheek and administer to give the dose slowly. Swirl-Pour an additional a further 2mL of water into the dosing cup, draw it into the syringe, and administer the remaining volume give it all to the infant. Wash cup and syringe thoroughly. Wash the dosing cup immediately after administration, allow to dry and store for the next use

After intensive PK sampling in Stage I and in Stage II each tablet can continue to be dispersed as described above or each tablet can be placed directly on the tongue and directly swallowed. Dispersible tablets may be given as multiples (up to a maximum of 6 tablets), depending on the weight of the child. Once dispersed, the medication should be consumed from administered using the supplied dosing cup or syringe, as soon as possible, preferably within 5 five minutes but no longer than 30 minutes after preparation.

5. In Appendices IA, IB, IC, ID, and IG, footnote for chemistries, the following updates are incorporated to clarifies guidelines for establishing a laboratory normal value for indirect bilirubin:

Electrolytes (sodium, potassium, and HCO3), glucose, creatinine, lipase, phosphorus, and LFTs. LFTs should include total bilirubin, indirect bilirubin, direct bilirubin, alkaline phosphatase, AST, ALT, and albumin. If indirect bilirubin is not reported by the site laboratory, it should be calculated at the site and documented. **The following formula can be utilized: indirect bilirubin = total bilirubin – direct (or "conjugated") bilirubin.**

The following (listed in order of preference) should be used to determine the upper limit of normal (ULN) values for indirect bilirubin.

- a. "ULN" values reported by the laboratory report for the test, or
- b. "ULN" values routinely used/established by the site or
- c. 'ULN" values as per the **most current** Harriet Lane Handbook (e.g. the current "ULN" for indirect bilirubin as per Harriet Lane Handbook is 0.4) (In the 2018 version of the Harriet Lane Handbook, for a full term infant, the ULN for total bilirubin is 1.2 mg/dL (21μmol/L) and for direct bilirubin is 0.2 mg/dL (3.4 μmol/L); thus the ULN for indirect bilirubin would be 1.0 mg/dL (17.6 μmol/L)).

C. Operational Guidance from Protocol CM #3, dated 31 March 2020

This CM provides operational guidance to study sites from the IMPAACT P1093 Protocol Team. The Protocol Team acknowledges that the extent to which site operations may be disrupted by the COVID-19 pandemic may vary across sites and over time. All sites should follow applicable government, health authority, and institutional policies with respect to conduct of study visits and procedures, with utmost importance placed on the health and well-being of study participants and study staff. Site investigators should continue to follow current protocol specifications for communication with the Protocol Team and should contact the team ([contact]) with any questions or concerns regarding this CM or management of study participants.

Visit Scheduling

- Sites that anticipate operational disruptions or closures in the near future are advised to conduct study visits early in the allowable visit window. Visits conducted prior to opening of the allowable window would also be preferred to completely missing a visit.
- Sites that are currently experiencing operational disruptions or closures are advised to conduct study visits late in the allowable visit window. Visits conducted after closing of the allowable window would also be preferred to completely missing a visit.
- Effective with the issuance of this CM, allowable windows are broadened as follows:

Appendices IA, IB, IC and ID (All Cohorts, Stage I and Stage II)

- Weeks 4, 8, 12 and 16 Visits: ± 2 weeks
- Week 24 Visit -6 to +4 weeks
- Weeks 32 and 40 Visits: ±4 weeks
- Week 48 Visit -4 to +6 weeks

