and PK guidelines. Failure with respect to the safety and/or PK guidelines will result in a dose adjustment within this cohort, with the starting dose adjusted in the appropriate direction, if this is feasible. New participants will be started on the new dose and evaluations will proceed as described above. If the Protocol Team deems a given participant's PK data to be unevaluable (e.g. because of reported non-adherence or PK results that would be physiologically implausible with good adherence), that participant will be replaced for dose finding purposes (but will continue in the study and contribute to the safety analyses). Note that the participant would be replaced for evaluating safety, as well as PK, criteria, if unevaluable PK data reflect uncertainty about appropriate exposure to the study medication. Once the dose finding procedures of Stage I have been completed for each cohort, the Protocol Team will review all safety and PK data and will make final recommendations concerning the doses. These recommendations will be reviewed by the Protocol Team. The purpose of this review process will be to take account of all available information in determining whether the dose finding algorithm has converged on the best dose for further study in Stage II or whether adjustments are needed. As part of this review process, safety and PK data will be broken down on the basis of the dosing adjustments that have been made because of the inducing or inhibiting effects of the background regimens. If there is evidence that some adjustments may have been associated with undesirable PK levels or with safety concerns, these adjustments may be modified for Stage II or further data may be gathered prior to opening Stage II. Under Version 5, the Stage I data from Cohorts III-DT, IV-DT and V-DT will also be examined by weight band. If this examination suggests that the dose under evaluation is not adequate for a given weight band and should not be used for that weight band in Stage II, then a new "weight band group" will be opened to determine an adequate dose for that weight band, and this weight band group will be evaluated like an age cohort, as described above. Participants accrued to Stage II of the study will be administered the doses determined for their age cohorts, with no individual dose adjustments on the basis of PK allowed. For purposes of analysis, data from these participants will be combined with the data from the Stage I participants who have been treated at the optimal doses determined for their cohorts and who have not required individual PK determined dose adjustments, such that their total exposure to the study drug has been at the optimal dose.

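### After rifampin stops, Section 6.1.8 keeps participants on EFV, FPV/r or TPV/r off once-daily DTG, but the matching Appendix IG sentence makes no exception

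*Protocol*

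**What the plan says.** LoA Section B, item B.3, amends Section 6.1.8 and Appendix IG together. Its stated aim is "to clarify the timeline for resuming once daily dosing of dolutegravir after discontinuation of rifampin-containing tuberculosis treatment". The item then prints one sentence for each place.

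- **Section 6.1.8** (the part on TB co-infection; second sentence of the final bullet): after rifampin-containing therapy ends, the participant's "DTG dose will revert back to once daily administration unless on EFV, FPV/r, or TPV/r".
- **The appendix** ("Appendix IG, note directly following Schedule of Evaluations, third sentence"): after the same event, the participant's "DTG dose will revert back to once daily administration". The sentence ends there.

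The LoA's Implementation paragraph says that changes are shown "using strikethrough for deletions and bold type for additions where appropriate". The SAP, under Pharmacokinetic Study Design, says that Stage I safety and PK data will be broken down by "dosing adjustments that have been made because of the inducing or inhibiting effects of the background regimens". It does not name EFV, FPV/r or TPV/r there.

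**The concern.** One dosing rule is issued in two places, with an exception in only one of them. LoA Section C (Visit Scheduling) labels Appendix IG as the schedule for participants who start rifampin, so it is a natural place for site staff to look when rifampin is stopped. Its reprinted sentence is unconditional. Read alone, it would move a child on EFV, FPV/r or TPV/r to once-daily DTG, which Section 6.1.8 says should not happen.

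What is at stake is under-dosing of DTG in those children. LoA Section C (Study Drug Supply) also allows dose changes for weight gain to be given by telephone when visits cannot take place. That is a different trigger, but it shows that dosing instructions may be carried out remotely, and sites then rely on the written rule.

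**Working it through.** The plan gives no figure to reproduce. The check is a comparison of two sentences, followed by a conditional calculation of dose.

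**1. The two sentences side by side**

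| Element | Section 6.1.8 | Appendix IG note, third sentence |
|---|---|---|
| Trigger | Rifampin-containing TB therapy discontinued | Same |
| Timing wording | Two alternatives run together (a lag of about two weeks; immediately upon stopping) | Same |
| Action | DTG returns to once daily | Same |
| Exception | EFV, FPV/r, TPV/r (3 regimens) | None (0 regimens) |
| Cross-reference to the other place | None | None |

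The wording is the same up to the words for once-daily administration. The exception is the only difference. No other part of the supplied documents mentions these three regimens or adds the exception to Appendix IG.

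**2. Is this old text against new text?** No. Both sentences are issued in the same item of the same LoA, so the comparison is not between an amendment log and the current protocol.

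**3. Could the exception have been struck out of Section 6.1.8?** Strikethrough is lost in the extracted text, so there are three possibilities:

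- *Retained text.* The mismatch stands.
- *Added text.* The mismatch stands more strongly: the exception was put in one place and missed in the other.
- *Deleted text.* The mismatch disappears.

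Deletion fits worst. The item says that it clarifies the timeline, and the two alternative timing phrases, which appear in both sentences, fully account for such a change. Removing a drug-specific exception would be a substantive dosing change outside that purpose. The SAP's reference to dosing adjusted for background regimens also suits an exception of this kind, though it is only indirect support.

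**4. Size of the dose change for an excepted child.** The dosing frequency during rifampin is not printed in the supplied text. Reverting to once daily implies *k* ≥ 2 doses a day beforehand. Let *r* be the amount per dose after the change divided by the amount before it. Then

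fall in daily dose = 1 − *r*/*k*.

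- *r* = 1 (assumed), *k* = 2: 1 − 1/2 = 50%.
- *r* = 1, *k* > 2: more than 50%.
- *r* = 2, *k* = 2: 1 − 2/2 = 0%. The total is kept only if the single dose is doubled, and neither sentence says to do that.

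**5. Reach into the analysis.** Under Pharmacokinetic Analyses, the SAP places intensive PK sampling between days 5 and 10 after study drug initiation. No stated statistical figure depends on the rule for stopping rifampin.

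**The case against.** The strongest objection is that most of the relevant text is missing. The LoA reprints one sentence of Section 6.1.8 and one sentence of the Appendix IG note. The rest of the note, the schedule table and its footnotes are not supplied, and any of them could carry the exception or point to Section 6.1.8. **This stands as a limit.** The dosing consequence therefore holds only if the unseen text does not supply the exception. Even if it does, the reprinted sentence is unconditional and a pointer would still help.

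The second objection is that the lost strikethrough leaves the status of the exception uncertain. **This stands in principle.** The text alone cannot settle it, but the item's stated purpose makes deletion unlikely.

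The third is that a specific rule in the TB management section should govern a general note to a schedule, and that sites implementing item B.3 see the two sentences one after the other. That is a sensible way to reconcile them, but it relies on staff consulting both places at the moment rifampin stops. A dosing rule should not need that.

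The fourth is that the magnitude is hypothetical. **This stands in part.** No document says whether any participant took rifampin together with one of these regimens, and the halving of daily dose assumes an unchanged amount per dose.

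**Conclusion.** The inconsistency holds as stated: Section 6.1.8 excepts three background regimens from the return to once-daily DTG, and the matching Appendix IG sentence excepts none. It should be corrected, because it concerns a dosing instruction in children. Confidence is medium.

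The conclusion about dosing rests on two conditions: that the exception in Section 6.1.8 is live text, which is the natural reading, and that no unseen part of Appendix IG supplies it, which cannot be checked here. The size, at least a 50% fall in daily DTG for an excepted child, further assumes the same amount per dose. The number of children exposed is unknown. The point is one of participant safety and of consistency between two instructions, not of design, sample size or analysis.

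**What to change.** Check the full Appendix IG note, then end its third sentence with the exception already used in Section 6.1.8 (EFV, FPV/r, TPV/r) and a reference to that section, so that both places give one rule. If the exception already appears elsewhere in the appendix, the addition does no harm. If the sponsor did mean to delete it from Section 6.1.8, the next document should say so explicitly, since that would be a dosing change and not a clarification of timing.

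The cost is one clause in the next clarification memo or LoA, with no change to design, sample size or analysis.

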Appendix IE (Long-Term Follow-up)

- Week 60 through Week 180 ±6 weeks
- Week 192 Visit -6 to +12 weeks

Appendix IF (Premature Discontinuation of Dolutegravir)

- Week 4 Follow-Up Visit: -2 to +4 weeks
- Every three months until resolved (if applicable): ± 6 weeks

Appendix IG (Participants who Start Rifampin)

- Week 2 Visit ±2 weeks
- Week 4 Visit -2 to +4 weeks
- Week 12 and Every 8 weeks until end of rifampin therapy Visits: ±4 weeks

Prioritization of Study Visit Procedures

- Sites with full capacity to conduct study visits in-person at the study clinic should continue to do so in full compliance with the protocol.
- Sites may also conduct study visits in full or in part off-site if permitted by applicable government, health authority, and institutional policies. Where this option is permitted, site staff should communicate with the parent/legal guardians to determine in advance where and when such visits will take place, with adequate protections for safety, privacy, and confidentiality. Off-site visit procedures should be conducted by site staff who are adequately qualified and trained to conduct the procedures, as determined by the site Investigator of Record (IoR), with attention paid to occupational health, biohazard containment, and specimen and data chain of custody. These staff should also be adequately qualified and trained to immediately assess and/or manage any adverse events or social

- impacts that may occur during the visits. If adverse events requiring further evaluation or management are identified during an off-site visit, staff conducting the visit should arrange for appropriate clinical management, in consultation with the IoR or designee as needed.
- Sites with limited capacity to conduct in-person scheduled study visits should prioritize monitoring for adverse events and provision of study drug. With respect to specimen testing and storage, sites should follow the priority listing in the relevant Schedules of Evaluations. At sites where specimen collection and processing can be performed per the Laboratory Processing Chart, but HIV-1 RNA testing cannot be performed in real time, sites may collect, process, and store specimens for later testing (alternate laboratories must adhere to local regulations for clinical laboratory testing).
- Sites with no capacity to conduct in-person visits, either on-site or off-site, should consider whether any study procedures (e.g., history taking, adherence assessment) can be performed remotely (e.g., by telephone). If adverse events requiring further evaluation or management are identified during a remote contact, staff conducting the contact should arrange for appropriate clinical management, in consultation with the IoR or designee as needed.

Study Drug Supply

- To avoid gaps in drug supply between visits, sites may dispense up to three months' supply of study drug, ensuring safety monitoring and addressing potential needs for dose modification due to weight gain. Further considerations are as follows:
 - Participants who have been dispensed an extra supply of study drug should still come for their scheduled visits, if possible.
 - If a participant is expected to grow into a higher weight band requiring a dose increase soon, sites should ensure accurate contact information with the family; if an in-person visit is not possible, study drug dose modifications may be implemented with dosing instructions provided to the participant's caregiver by telephone based on weight reported by the caregiver. Any such instruction should be source documented in the participant's study chart.
 - Sites should also make every effort to ensure adequate supplies of the other antiretroviral agents that comprise participants' optimized background treatment regimens.
- Where feasible, sites are encouraged to implement study drug delivery options involving outdoor pick- up or drop-off. Where outdoor pick-up or drop-off is not feasible, the *Pharmacy Guidelines and Instructions for DAIDS Clinical Trials Networks* permit shipment or courier of study drug from the site directly to participants. This method should only be used in the short-term and if permissible per local institutional and IRB/EC policies. Refer to the *Guidelines* for additional details on this method.
- Sites are encouraged to provide adherence assessment, counseling, and support remotely (e.g., by telephone).

Documentation

- Site-specific contingency plans, and the implementation thereof, should be documented in essential document files for IMPAACT P1093.
- Documentation should be entered in participant study charts in real-time should any of the following occur:
 - Missed visits
 - Out-of-window visits
 - Off-site visits (document the location of the visit)
 - Incomplete or partial visits (document which procedures were performed and which were not)
 - Remote contacts performed in lieu of in-person visits (document method used to complete the contact and which procedures were performed)
 - Any other participant contacts

- Use of alternate laboratories or alternate laboratory assays
- Alternate provision of study drug
- Dose modifications implemented remotely
- In consultation with the Division of AIDS, the IMPAACT Network is developing comprehensive guidance for documenting and/or reporting protocol deviations that may occur due to limited site capacity to conduct study visits or procedures during the COVID-19 pandemic. Similar guidance will be provided for documentation of use of alternate laboratories or alternate laboratory assays. Once this Network-level guidance is available, it will be provided in a separate communication to all sites.
